1.1 Background and Rationale

The human papillomavirus (HPV) vaccination coverage rate in Switzerland is below the target rate of 80% that has been set as a goal by the ministry of health. We assume that a multifaceted, targeted educational intervention with focus on teaching a presumptive announcement recommendation style on general practitioners (GPs) results in an increase of HPV vaccination (HPVv) rates in Swiss primary care.

1.2 Hypotheses

The primary study hypothesis is that a multifaceted, targeted intervention with a focus on teaching a presumptive announcement recommendation style will result in an increase of HPVv rates of patients aged 18 years and older in Swiss primary care. The analyses presented in this document will assess the efficacy of such an educational intervention aimed at GPs will be included in the final study report.

2 Study Methods

2.1 Trial Design

2.1.1 Study Population

The study population will consist of GPs working in practices in German-speaking Switzerland. Fulfilment of all inclusion-exclusion criteria will be reviewed by the investigator or qualified designee to ensure that subjects qualify for the study.

Inclusion criteria:

- i) The GP works in the primary care setting.
- ii) The GP has been providing vaccinations according to the Swiss ministry of health (recommended basic and recommended additional vaccinations) for at least six months in their practice before study start. In detail: combined measles, mumps and rubella (MMR), meningococci, pneumococci, HPV, tick-borne encephalitis (TBE), chickenpox, shingles, and hepatitis A/B (combination and single vaccinations).

Exception: GPs not registered in the cantonal HPVv program can be included if they are willing to join the programme and have the eligible patient population in their practice to administer vaccinations.

Note: 'Providing vaccinations' means that a GP (or the practice they work at) in principle offers the vaccination to the patients. There is no need for a minimum number of vaccinated patients in the last six

months before inclusion into the study. For example, GPs registered in the cantonal HPVv program can be included even if they have not administered any HPVv doses during the previous six months.

Exclusion criteria:

- The GP predominantly provides pediatric care (reported by the GP as >50% of consultations).
- The GP predominantly provides gynecological care (reported by the GP as >50% of consultations).
- The GP is a school physician or provides vaccinations on behalf of schools.

2.1.2 Interventions

This study will comprise two arms:

- Control intervention group: Participants will receive a general educational session about vaccinations, with no special focus on HPVv. Study participants allocated to this group will be blinded to the aim of the study to increase HPVv specifically.
- Active intervention group: Participants will receive an educational session that comprises a targeted, multifaceted intervention. It will consist of i) basic information about HPV and HPVv, ii) information about the announcement communication method in delivering vaccinations, and iii) information about logistics and administrative issues regarding the HPVv. In addition, this educational session will include the same general information about vaccinations as delivered in the control intervention group.

2.2 Randomization

Randomization will occur cluster-wise on level of the practices where the enrolled GPs work. A statistician external to the study group will carry out stratified randomization into the active or control intervention group using the Shiny Balancer tool, which facilitates balanced allocation in cluster-randomised trials (1).

Stratification will occur according to the following factors:

- Participation status in the cantonal HPVv program at inclusion (yes/no).
- Estimated number of HPVv administered during the baseline period (4 categories, see section 3.3.1).

GPs enrolling in the trial when randomization of their practice has already taken place will be allocated to the corresponding study arm. GPs will need to be registered in the cantonal HPVv program before initiation of outcome measurements.

2.3 Blinding

All study participants will be blinded to the respective other intervention. Study participants in the control intervention arm will be entirely blinded to HPVv being the specific topic of the study (i.e., all CRFs and questionnaires will ask information about HPVv together with information about other vaccinations, without emphasis on HPVv).

2.4 Sample Size

According to the study protocol (2), a sample size of 33 GPs, each recruiting 30 patients, will achieve a power of 80% at an alpha of 5% to detect a coverage change of +9.5% in the control group and of +14.9% in the active intervention group (according to a similar study (3))

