3.1 Confidence Intervals and *p*-Values

We will report statistical significance as determined in statistical null hypothesis tests by means of p-values. A level of significance of 0.05 will be used throughout the analyses. Accordingly, we will report two-sided 95% confidence intervals of coefficient estimates.

We will use a mixed-effects regression model for assessment of the primary objective and we will base rejection of the null hypothesis (no difference in effect on HPVv counts at T6 between the control and

intervention group related to the study hypothesis (see section 1.2) on statistical significance of a specific fixed effect coefficient estimate (see section 4.2.3).

Secondary outcomes will be assessed in an exploratory manner, and no adjustment for multiplicity will be implemented. We will judge resulting *p*-values with appropriate caution and consider the corresponding effect sizes.

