3.3.2 Outcome Measurements

GPs will document all vaccines administered to patients aged at least 18 years starting on T0 and ending on T12. We will provide enrolled GPs with separate standardized case report forms (CRFs) to report all vaccinations administered during the study period and the follow-up period, respectively. GPs will report the following vaccinations: HPV, MMR, meningococci, pneumococci, TBE, chickenpox, shingles, and hepatitis A/B (combination and individual vaccines). The GPs will send CRFs to the Institute of Primary Care every two months by mail. For the study period and the follow-up period, GPs will report age and sex of patients to whom these vaccines are administered. In addition, only during the study period, they will report whether vaccinations are administered as first/second/third doses or as booster vaccinations as well as whether they are administered upon request by the patient or as recommended by the GP. During the follow-up period, they will only indicate whether vaccinations are administered as first or later doses (without further specification).

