4.1 Objective Definitions

4.1.1 Primary Objectives

(1) To compare the first-dose HPVv counts at T6 between the intervention group and the control group.

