4.2.3 Analysis of the Primary Objective

To analyze the primary objective, we will model the count of first administered HPVv doses at T6 using mixed-effect Poisson regression. The outcome variable will be the count of first HPVv doses administered by each GP at each of the time points T3 or T6. GP-level random intercepts will account for intra-GP correlation. The following fixed effects will define the grouping variables of the data set:

- Study arm (binary with levels control; active)
- Time point (binary with levels T3; T6)
- Baseline HPVv count (categorical with levels Never; Rarely (1–5 doses); Occasionally (6–10 doses); Regularly (at least 11 doses))
- GP gender (binary with levels male; female)
- GP age in years (continuous)
- GP workload (categorical with levels < 60%; 60–79%; 80–100%; based on the distribution of consultation counts according to workload in Swiss primary care (4))
- GP participation status in the cantonal HPVv program at inclusion (binary with levels yes; no)
- Patient gender (binary with levels male; female).

Each fixed effect other than the study arm will be included in the final model if a corresponding univariate analysis results in a *p*-value ≤ 0.2 .

The Poisson regression model will be assessed for overdispersion based on an asymptotic chi-squared test for the sum of squared residuals (5, 6). If the null hypothesis of no overdispersion is rejected at the 0.05 level, we will replace the Poisson model by a negative binomial model with the same fixed- and random-effect structure. A quasi-Poisson model will be considered as an alternative in case of an observed linear variance-to-mean relationship (7).

Rejection of the null hypothesis related to the primary objective (the effect associated with the study arm is equal to zero) will be based on the parameter estimate of study arm and its 95% confidence interval in the final model.

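### The 80% power in SAP section 2.4 belongs to a patient-level coverage comparison, not to the per-GP first-dose count that is tested, and it does not reproduce under the SAP's own two-sided test

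*SAP*

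**What the plan says.** Section 2.4, citing the study protocol, states that "a sample size of 33 GPs, each recruiting 30 patients, will achieve a power of 80% at an alpha of 5" per cent, and gives the effect as "to detect a coverage change of +9.5% in the control group and of +14.9% in the active intervention group". It does not say whether 33 is the total or the number per arm, whether the test is one- or two-sided, or what allowance was made for clustering.

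Other sections fix the following:

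- **Randomisation (2.2):** practices, not GPs or patients, are randomised.
- **Inference (3.1):** "A level of significance of 0.05 will be used throughout the analyses", and "we will report two-sided 95% confidence intervals of coefficient estimates". Under section 4.2.3 the primary decision "will be based on the parameter estimate of study arm and its 95% confidence interval in the final model".
- **Data (3.3.2):** "GPs will document all vaccines administered to patients aged at least 18 years starting on T0 and ending on T12".
- **Primary objective (4.1.1):** "To compare the first-dose HPVv counts at T6 between the intervention group and the control group". Section 4.2.3 models this as a count per GP by mixed Poisson regression, with a negative binomial fallback.
- **Changes to the protocol (7):** the outcomes become absolute uptake after T0 instead of change from T0. No change to the sample size is listed.

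**The concern.** The power statement and the primary test concern different quantities. Section 2.4 compares proportions of patients, 30 per GP. The primary analysis compares numbers of first doses per GP. The SAP describes recording of vaccines given, not of eligible patients who stay unvaccinated, so no proportion covered can be formed. The 30 recruited patients per GP appear nowhere outside section 2.4.

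Power for a count depends on the expected count, the variance between GPs and the variance between practices. Section 2.4 gives none of these.

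If the sentence stands, the final report may carry an 80% power claim that was never worked out for its primary test, and a null result could be read as firmer evidence of no effect than it is.

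**Working it through.** **1. Reproducing the 80% under the SAP's own test.** Inputs from section 2.4: p1 = 0.095, p2 = 0.149, 33 × 30 = 990 patients. Two-sided 5% comes from section 3.1. Equal arms are assumed.

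With n patients per arm and p̄ = 0.122,

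power = Φ{[(p2 − p1)√n − z√(2p̄(1 − p̄))] / √(p1(1 − p1) + p2(1 − p2))},

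where √(2p̄(1 − p̄)) = √0.2142 = 0.4629 and the denominator is √0.2128 = 0.4613.

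- 33 GPs in total, n = 495: (0.054 × 22.25 − 1.96 × 0.4629) / 0.4613 = 0.638, so power is **73.8%**.
- 33 GPs per arm, n = 990: (0.054 × 31.46 − 1.96 × 0.4629) / 0.4613 = 1.717, so power is **95.7%**.

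For 80% power the same method needs 576 patients per arm. 576/30 = 19.2, hence 20 GPs per arm or 40 in total, before clustering.

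**2. Clustering.** The SAP gives no intracluster correlation (ICC), so these values are assumed. The design effect is 1 + 29 × ICC, with the GP as the cluster. It divides n.

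| Assumed ICC | Design effect | Power, 33 in total | Power, 33 per arm |
|---|---|---|---|
| 0 | 1.00 | 73.8% | 95.7% |
| 0.01 | 1.29 | 62.8% | 89.9% |
| 0.02 | 1.58 | 54.2% | 83.2% |
| 0.05 | 2.45 | 38.1% | 65.0% |

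**3. What recovers 80%.** Two routes were found on these proportions, and each needs inputs that section 2.4 does not state.

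- *Two-sided, 33 per arm:* 990/575.5 = 1.720, so ICC = 0.720/29 = 0.025.
- *One-sided with continuity correction, 33 in total, no clustering:* [(0.054 − 1/495) × 22.25 − 1.645 × 0.4629] / 0.4613 = 0.857, so power is 80.4%. The required 490 per arm gives 980/30 = 32.7, which rounds up to 33 GPs. This route conflicts with the two-sided intervals of section 3.1 and ignores the cluster randomisation of section 2.2. Without the continuity correction, one-sided power is 83.0%, and an ICC of 0.003 brings it to 80%.

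Reading the percentages as gains on top of an existing coverage also changes the result. At an assumed starting coverage of 10%, two-sided power without clustering is 53% (33 in total) or 82% (33 per arm). That starting value is not stated either.

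**4. Illustration for the count outcome.** Everything here is assumed, because the SAP gives no expected count or variance. The rate ratio is 14.9/9.5 = 1.57 (log 0.450). μ is the control mean of first doses per GP over six months, 2 to 20. The between-GP dispersion k is 0.25 to 1. n is GPs per arm (16.5 or 33). Practice clustering and covariate adjustment are left out.

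SE(log RR) = √[(1/μ + k)(2/n)]; power = Φ(0.450/SE − 1.96); detectable ratio at 80% power = exp(2.80 × SE).

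| GPs in total | μ, k | SE | Power | Detectable ratio |
|---|---|---|---|---|
| 33 | 2, 1 | 0.426 | 18% | 3.3 |
| 33 | 20, 0.25 | 0.191 | 66% | 1.7 |
| 66 | 2, 1 | 0.302 | 32% | 2.3 |
| 66 | 10, 0.25 | 0.146 | 87% | 1.5 |
| 66 | 20, 0.25 | 0.135 | 92% | 1.5 |

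**The case against.** The strongest reply is that section 2.4 is a one-sentence summary of a calculation made in the protocol. The ICC, the sidedness and the meaning of 33 may all be given there, and an SAP need not repeat them. This stands: their absence is not itself an error. It does not remove the mismatch, because the SAP restates the 80% next to a different primary outcome and a two-sided test.

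Three stronger readings are tempting, and the document does not support them.

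- *A reader might infer that the 80% is an arithmetic mistake.* This is not shown. Two sets of assumptions reach it, so a claim that it works only with 33 per arm and an ICC of 0.025 would be false.
- *A reader might infer that coverage was the protocol's endpoint and has been superseded.* Section 7 says only that change from T0 was dropped and that baseline counts became categorical. Its mention of a precise number of vaccinations suggests that the protocol may already have used dose numbers. The original endpoint cannot be checked.
- *A reader might infer that the primary test is underpowered.* Its power is unknown. With 66 GPs, a high mean and low dispersion it exceeds 80%. Baseline vaccination category is a stratification factor and a candidate covariate, which would reduce the between-GP variance; practice clustering would work the other way.

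It is also fair that inference rests on an estimate with its 95% confidence interval, so imprecision would show in a null result. That limits the harm without making the power statement correct.

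**Conclusion.** The point holds as an inconsistency. The mismatch between section 2.4 and sections 3.3.2, 4.1.1 and 4.2.3 needs no assumption: the stated 80% concerns a patient-level coverage change and cannot be attached to a comparison of first-dose counts per GP. Section 7 alters the outcome without returning to the sample size.

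The second part is narrower: the figure does not reproduce as written. The two-sided results rest on equal arms, on treating 9.5% and 14.9% as simple proportions, and on no clustering.

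The count-outcome range rests wholly on assumed inputs. It shows how widely power could vary, not what this trial's power is. The correction should be made before the final report, but it changes no analysis or estimate.

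**What to change.** Revise section 2.4 in one paragraph.

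1. Say that the 80% belongs to the coverage calculation and does not describe the first-dose count.
2. Reconcile that calculation with the two-sided test and practice randomisation: 33 in total or per arm, sidedness, and the ICC used, taken from the protocol if given there.
3. Give the detectable rate ratio for the primary count model at the enrolled numbers of GPs and practices, over a stated range of mean counts and of between-GP and between-practice variances.
4. Note in section 7 that the sample size was not recalculated for the count outcome.

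This needs a short calculation and no extra enrolment. The downside is a stated power that is likely to look less favourable.

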2.5 Framework

This study is conceptualized as a superiority trial aiming to detect a difference between the active and the control intervention.

2.6 Statistical Interim Analysis and Stopping Guidance

Due to the lack of risks associated with the study interventions (2), we will include no stopping criteria nor interim analyses.

2.7 Timing of Final Analyses

We will perform a preliminary descriptive analysis of baseline characteristics of the study population upon transfer of the baseline data of the last included GP into OpenClinica. The final analysis of the study will be conducted after transfer of the last CRF into OpenClinica and after finalization and approval of this SAP.

2.8 Timing of Study Assessments

For each GP included into the study, we define the following timings:

- Baseline period Pb: A consecutive period of three months as recent as possible, but entirely before the intervention date Ti. Study participants will be asked to provide estimates of the number of HPVv doses administered during this period, which will be used for stratified randomization (see sections 2.2 and 3.3.1).
- Intervention date Ti: The day of delivery of the active and control intervention in the active intervention arm or of the control intervention in the control intervention arm. A questionnaire assessing knowledge on HPV and attitudes concerning HPVv will be administered at Ti, right before delivery of the intervention.
- Study start T0: The day of start of vaccination counting, usually scheduled on the 1st of the respective month following Ti. If Ti falls within the first week of a month, T0 is usually scheduled on the 15th of the same month.
- Follow-up at T3, T6, and T12: The dates at three, six and twelve months, respectively, after the study start T0. The questionnaire on HPV knowledge and HPVv attitudes will be delivered a second and final time at T6.
- **Study period**: The time interval between T0 and T6, which is the time interval relevant to the primary objective of the study.
- Follow-up period: The time interval between T6 and T12.
- Study end: The follow-up date T12, which indicates the end of all vaccination documentation.

3 Statistical Principles

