4.2.6 Subgroup Analyses

We will conduct a subgroup analysis for the baseline HPVv count by repeating the primary outcome analyses on data sets restricted to the categories of baseline HPVv count as defined in section 3.3.1. We will report the estimated coefficients together with 95% confidence intervals.

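### For GPs who join after their practice was randomised, the baseline period can fall after allocation and after colleagues' training

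*SAP*

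**What the plan says.** Timings are set GP by GP: section 2.8 opens its list with "For each GP included into the study, we define the following timings". Pb is then "A consecutive period of three months as recent as possible, but entirely before the intervention date Ti". The same bullet says that GPs estimate their HPV doses for this period, "which will be used for stratified randomization (see sections 2.2 and 3.3.1".

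Allocation works at another level. Section 2.2 states "Randomization will occur cluster-wise on level of the practices where the enrolled GPs work" and lists as a stratification factor "Estimated number of HPVv administered during the baseline period (4 categories, see section 3.3.1". It then provides for later entrants: "GPs enrolling in the trial when randomization of their practice has already taken place will be allocated to the corresponding study arm".

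The Pb category is used three more times:

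- Section 4.2.3 lists it as a candidate fixed effect in the primary model ("Baseline HPVv count (categorical with levels Never", and so on through the four categories), retained if its univariate p-value is at most 0.2.
- Section 4.2.6: "We will conduct a subgroup analysis for the baseline HPVv count by repeating the primary outcome analyses", restricted to each category.
- Section 4.2.4, secondary objective 3, takes it as the reference against which an increase at T6 is judged.

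Section 7 records that the outcomes are no longer changes from baseline but absolute uptake. The Pb category is therefore the only measure of a GP's earlier vaccination volume that remains available to the primary model.

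**The concern.** A baseline covariate should be fixed before allocation, or at least be beyond its influence. Here the limit on Pb is the GP's own session, which for a late joiner comes after the practice's allocation and may come well after colleagues' session. The instruction to take the most recent window pushes Pb toward that session.

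If working beside trained colleagues changes a GP's HPV vaccination before their own session, a late joiner in an active practice reports a raised Pb. A late joiner in a control practice has no comparable source. Three things would follow:

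- **Primary model.** Adjusting for a category that already carries part of the intervention removes part of the effect.
- **Subgroups.** The strata would be formed partly on a variable affected by treatment. Within a category, the affected active GPs would have lower underlying activity than the control GPs beside them.
- **Secondary objective 3.** A raised reference makes an increase harder to show, in the active arm only.

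**Working it through.** **Step 1. Who is protected by the text.**

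| GP | Does Pb feed the stratification? | Upper limit on Pb from the text |
|---|---|---|
| Present when the practice is randomised | Yes (2.2, 2.8) | Randomisation, by implication, because the count must exist to be used |
| Enrols after the practice was randomised | No, takes the practice's arm (2.2) | Own Ti only (2.8) |

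No section says that Pb must end before the practice's randomisation. Table 1 would not settle it: the marks in its cells were not legible in the text reviewed, but its caption defines the inclusion period as running up to delivery of the intervention. A mark in that column would not tie Pb to the randomisation date.

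**Step 2. How much of a late joiner's Pb can follow colleagues' training.** Take three months as 13 weeks, and let t be the weeks between the colleagues' session and the late joiner's own Ti. The SAP gives no value for t. With the most recent window, the share of Pb after the colleagues' session is up to min(t, 13)/13:

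- t = 4: 4/13 = 31%
- t = 8: 8/13 = 62%
- t of 13 or more: 100%
- a late joiner who attends the same session as colleagues (t = 0): 0%

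**Step 3. What this could do to the adjusted primary effect.** The SAP has no figure to reproduce, so this is an illustration, and every input is assumed:

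- true rate ratio 1.5
- mean of 4 doses per three months, outcome counted over six months
- between-GP standard deviation of 0.8 on the log scale
- late joiners' Pb lies wholly after colleagues' training
- in active practices the late joiner's baseline rate is multiplied by 1 + s × (1.5 − 1), where s is the spillover: s = 1 gives 1.50 and s = 0.5 gives 1.25
- Pb is grouped as in section 3.3.1 (0, 1–5, 6–10, 11 or more doses)
- Poisson regression of the outcome on arm and Pb category, 200,000 simulated GPs per setting

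This is simpler than the planned model, with no GP random intercept and no other covariates. It shows direction and rough size only.

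| Late joiners | Adjusted rate ratio, s = 0.5 | Adjusted rate ratio, s = 1 |
|---|---|---|
| 0% | 1.50 | 1.50 |
| 10% | 1.48 | 1.46 |
| 25% | 1.44 | 1.39 |
| 50% | 1.40 | 1.31 |

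On the log scale, using the unrounded results, the loss is 1 − ln(1.457)/ln(1.5) = 7% at 10% late joiners with full spillover, and 1 − ln(1.394)/ln(1.5) = 18% at 25%. With half spillover the losses are 4% (1.477) and 10% (1.442). With no late joiners or no spillover there is no bias.

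**The case against.** The strongest reply is that section 2.8, read as a whole, already limits Pb: an estimate used for stratified randomisation has to exist beforehand. That is right for GPs present at randomisation. A reader might infer from the Ti anchor that the stratification itself rests on post-allocation data, or that every GP's analysed Pb overlaps the gap between randomisation and the session. The SAP supports neither. Section 3.3.1 describes one baseline question and no second collection, and late joiners' counts do not enter the stratification.

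Time after allocation is also not the same as exposure to the intervention. Before Ti a GP has received nothing, and section 2.3 blinds participants to the other arm's intervention. Bias therefore needs a chain: the GP joins after randomisation, is trained later than colleagues, reports a Pb that overlaps the interval, and changes HPV vaccination through contact with trained colleagues. The SAP does not mention such spillover, so it is an assumption here, though randomising by practice is commonly chosen to guard against just this.

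A reader might also suspect that GPs who join the cantonal HPV programme shortly before Ti distort the comparison. Section 2.2 imposes registration on both arms alike, and nothing suggests a difference by arm.

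Finally, Pb enters the primary model only if it passes the univariate screen, it is a coarse self-reported category, and secondary objective 3 is exploratory. These points limit the size. They do not give a late joiner's Pb an upper limit at randomisation.

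**Conclusion.** The point holds for late joiners only. The stated rule allows their baseline period to fall after their practice was allocated and, if they join after colleagues' session, after those colleagues were trained. That value can then enter the primary model, the subgroups and the reference for secondary objective 3.

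Any resulting bias in the primary effect is toward the null and probably modest: under the assumptions shown, a rate ratio of 1.50 becomes 1.46–1.48 with 10% late joiners. The larger shifts need a quarter or more of GPs to join late, with substantial spillover. The SAP gives neither quantity, so the actual size cannot be stated. This is a cheap improvement to the plan and does not undermine the randomisation.

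**What to change.** In section 2.8, state that Pb is the three-month period ending before the date the GP's practice is randomised, and that this applies equally to GPs who enrol later. In sections 4.2.3, 4.2.4 (objective 3) and 4.2.6, use only that value.

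Some late joiners will have no valid count for that window. Section 2.1.1 asks for six months of providing vaccinations before study start. A GP whose T0 falls more than 6 − 3 = 3 months after randomisation can meet that criterion without having worked in the practice for the whole window. For such GPs, or if the baseline forms are already collected, flag late joiners in the data set and repeat the primary analysis without them, as a sensitivity analysis beside the main one.

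The cost is one sentence, a fixed date range on the baseline form and possibly one extra analysis. Late joiners recall a slightly older period, and a few may have no baseline value. Under the complete-case rule in section 4.3 those few would drop out of any model that retains Pb, so their number should be reported.
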